3.0 Endpoints

3.1 Primary Endpoint

The primary efficacy endpoint is the change from baseline in the frequency of monthly migraine days across Months 5 and 6, which are defined as the 28-day daily diary periods ending with Days 56 and 84 after the second study treatment intervention day with BOTOX or placebo injections, for subjects in the intent-to-treat (ITT) population. Baseline is defined as the number of migraine days during the last 28 days prior to the randomization date.

3.2 Secondary Endpoints

[figure not shown]
The secondary endpoints of the Double-Blind Treatment Phase will be included in multiplicity adjustment of the Type I error to control the familywise error rate (FWER) at 2-sided significance level of 0.05 for the entire study. Each dose comparison will be

[figure not shown]
analyzed across primary and secondary endpoints in the order described in Section 13.0, using a ranked-order serial gatekeeping approach to control the overall type I (false positive) error rate.

[figure not shown]
1. Change from baseline in the frequency of monthly headache days across Months 5 and 6
2. Responder status of 50% reduction from baseline in the frequency of monthly migraine days across Months 5 and 6
3. Change from baseline in the frequency of monthly acute headache medication days across Months 5 and 6
4. Change from baseline in Migraine-Specific Quality of Life Questionnaire version 2.1 (MSQ v2.1) Role Function Restrictive (RFR) domain score at Month 6
5. Change from baseline in the Activity Impairment in Migraine Diary (AIM-D) Physical Impairment (PI) domain score across Months 5 and 6 (total 6-item Headache Impact Test [HIT-6] score for EU)

3.3 Additional Efficacy Endpoints

The primary and secondary efficacy endpoints included in multiplicity adjustment of the FWER are listed in Section 3.1 and Section 3.2, respectively. The primary and secondary efficacy measures will also be evaluated at monthly time points. The additional efficacy endpoints are:

3.4 Safety Endpoints

Safety endpoints are:

- Adverse events (AEs), serious AEs (SAEs) and possible distant spread of toxin (PDSOT)
- clinical laboratory testing (hematology, chemistry, and urinalysis)
- Vital sign measurements
- The Columbia-Suicide Severity Rating Scale (C-SSRS) scores

For clinical laboratory and vital sign parameters, the last non-missing safety assessment before the date of first dose of the study treatment will be used as the baseline for all analyses of that safety parameter.

All AEs and other safety data will be presented in the listings at the subject level.

4.0 Analysis Populations and Data Conventions

4.1 Analysis Populations

The following population sets will be used for the analyses.

The Intent-to-Treat (ITT) population includes all randomized subjects. This will be used as the full analysis set (FAS) population. The ITT population will be used for all efficacy and baseline analyses. Subjects will be included in the analysis according to the treatment group to which they were randomized (as randomized), regardless of study intervention received. (All subjects will have non-missing baseline data for the primary efficacy variable because it is a condition of randomization, and therefore, the ITT population is not being modified with such a constraint.)

The Safety Analysis Set includes all subjects who received any amount of study treatment. Subjects will be included in the analysis according to the study treatment that they actually received (as treated). A subject's actual treatment will be determined by the first dose of study treatment.

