2.0 Study Objectives and Design

2.1 Study Objectives

The objective for the double-blind phase is to evaluate the efficacy and safety of 2 dose levels of BOTOX compared with placebo as migraine prevention in EM subjects (defined as subjects with 6 to 14 migraine days and < 15 headache days per 28-day period).

The objective for the open-label phase is to evaluate the long-term safety of BOTOX as migraine prevention in EM subjects.

Clinical Hypotheses

- At least 1 dose level of BOTOX is more effective than placebo, as measured by the difference between treatment groups in the change from baseline in the frequency of migraine days per 28-day period
- BOTOX has an acceptable safety profile

[figure not shown]
The estimand corresponding to the primary efficacy endpoint is the difference in the change from baseline in the frequency of monthly migraine days across Months 5 and 6 between each BOTOX dose group and placebo in the intent-to-treat (ITT) population.

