Subjects who complete the double-blind, placebo-controlled phase may be eligible to continue to the open-label treatment phase of the study at Week 24 (V8). All subjects in the open-label phase will receive BOTOX 195 U at 12-week intervals for up to 2 treatment cycles.

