4.3.2 Direction of Differences

Treatment differences will be reported as higher dose minus lower dose (e.g., BOTOX 195 U minus BOTOX 155 U, BOTOX 155 U minus placebo and BOTOX 195 U minus placebo). In the open-label phase, all subjects will receive BOTOX 195 U, so the higher minus lower dose will be determined by the DBPC treatment component of the treatment regimen. Thus, treatment differences will mean BOTOX 195 U/BOTOX 195 U minus BOTOX 155 U/BOTOX 195 U, BOTOX 155 U/BOTOX 195 U minus Placebo/BOTOX 195 U, BOTOX 195 U/BOTOX 195 U minus Placebo/BOTOX 195 U (e.g., "BOTOX 195 U/BOTOX 195 U" represents subjects who receive BOTOX 195 U in both the double-blind and open-label phases of the study. "Placebo/BOTOX 195 U" represents subjects who cross over from placebo in the double-blind phase to BOTOX 195 U in the open-label phase.) Changes from baseline will be reported as follow-up minus baseline. A negative score for the change from baseline in frequency of headache days indicates improvement and a positive score indicates worsening.

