6.0 Study Treatment Duration and Compliance

For the Safety Analysis Set, duration of treatment exposure will be summarized for each treatment group and for total BOTOX group. Duration of treatment exposure is defined for each subject as last dose date minus first dose date + the minimum of [84 days or (exit visit date – last dose date plus 1)]. For this purpose, the duration is assumed to last 12 weeks after the last dose unless the subject exits the study sooner. This applies to the placebo group as well as to BOTOX groups. Duration of treatment exposure will be summarized using the number of subjects treated, mean, standard deviation, median, Q1, Q3, minimum and maximum. The number and percentage of subjects with treatment durations will be summarized in 12-week intervals (e.g., weeks: < 12, 12 to < 24, 24 to < 36, 36 to < 48 and \geq 48). In addition, the number and percentage of subjects treated in each treatment cycle (Day 1, Week 12, Week 24, and Week 36) will be summarized. Also, the number and percentage of subjects who are treated in at least 1, 2, 3 and 4 injection cycles will be summarized.

In addition to each 28-day diary window, daily diary compliance rates will be calculated, summarized as a continuous variable and compared between treatments for each injection cycle and over the whole study for the intent-to-treat population. Diary compliance will be determined by the subject's recording of data for a given day, either on that given day or for that given day during recall data entry the next day.

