10.0 Safety Analyses

10.1 General Considerations

In general, adverse events (AEs) data will be analyzed and presented for

1. The double-blind phase (i.e., AEs with start date or increase in severity on or after Day 1 through the last day preceding the Week-24 injection).
2. The open-label phase (i.e., AEs with start date or increase in severity on or after the injection day of the Week-24 treatment through Week 48 visit). Subjects who complete the double-blind, placebo-controlled phase to enter the open-label phase will be included in this analysis.
3. The entire post-injection study duration (i.e., AEs with start date or increase in severity on or after Day 1 through Week 48 visit).
4. Each treatment cycle (i.e., AEs with start date or increase in severity on or after day of injection through last day preceding subsequent injection of study treatment).

In each of cases 1-4 above, a specific AE will only count once per subject, associated with its worst severity during the time period of interest. Unless stated otherwise, the method of analyses described in this section will be applied to each of the 4 cases.

Safety data will be summarized for the Safety Analysis Set. Safety summaries will be presented by treatment group. For the safety analysis, participants are assigned to a treatment group based on the treatment actually received, regardless of the treatment randomized.

The safety parameters will include adverse events (AEs), clinical laboratory test results (hematology, chemistry and urinalysis), vital signs, C-SSRS, and concomitant medications and procedures. For clinical laboratory and vital signs, the last non-missing safety assessment before the first dose will be used as the baseline for all analyses of that safety parameter. Continuous variables will be summarized by number of participants and mean, SD, median, Q1, Q3, minimum, and maximum values. Categorical variables will be summarized by number and percentage of participants.

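### With the safety group fixed by first dose and no exposure split at Week 24, up to 24 weeks of open-label BOTOX 195 U per placebo-first subject falls in the placebo row of the whole-study exposure and adverse event tables

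*SAP*

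**What the plan says.** **Safety group.** SAP 4.1 places subjects in the Safety Analysis Set as treated and adds: "A subject's actual treatment will be determined by the first dose of study treatment". The sentence has no phase limit.

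**Open-label treatment.** SAP 2.3 states: "All subjects in the open-label phase will receive BOTOX 195 U at 12-week intervals for up to 2 treatment cycles". SAP 2.1 gives the purpose of that phase: "The objective for the open-label phase is to evaluate the long-term safety of BOTOX as migraine prevention in EM subjects".

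**Exposure.** In SAP 6.0, "duration of treatment exposure will be summarized for each treatment group and for total BOTOX group". The formula opens "Duration of treatment exposure is defined for each subject as last dose date minus first dose date + the minimum of [84 days or", and the alternative inside the minimum is exit date minus last dose date plus 1. Duration categories run up to 48 weeks or more. After stating that exposure is taken to last 12 weeks beyond the last dose unless the subject exits sooner, the section says: "This applies to the placebo group as well as to BOTOX groups". It does not define total BOTOX and does not mention Week 24 as a break.

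**Adverse events.** SAP 10.1 presents safety by treatment group over four periods: double-blind, open-label, entire study, and each cycle. The third is "The entire post-injection study duration (i.e., AEs with start date or increase in severity on or after Day 1 through Week 48 visit".

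**Regimen labels.** SAP 4.3.2 does name treatment sequences. Its Placebo/BOTOX 195 U label "represents subjects who cross over from placebo in the double-blind phase to BOTOX 195 U in the open-label phase". That section concerns the sign of treatment differences. SAP 4.1, 6.0 and 10.1 do not adopt its labels for safety or exposure columns.

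**The concern.** The first-dose rule works while each subject stays on one treatment. From Week 24 that no longer holds: continuing placebo-first and 155 U-first subjects both move to 195 U. A single lifelong label combined with an exposure clock that runs from first to last dose credits the later 195 U time to the earlier group.

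Two outputs span the switch and are affected: the exposure summary in SAP 6.0 and the entire-study adverse event summary, the third period in SAP 10.1. Both bear on the open-label objective of long-term BOTOX safety. The placebo exposure row would overstate time on placebo, the 155 U row would contain 195 U time, and total BOTOX could be too small. Any rate per subject-year that used these totals as its denominator would carry the error.

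**Working it through.** **Inputs from the documents**
- 259 subjects per arm (SAP 2.4; 3 × 259 = 777).
- Injections at Day 1 and Weeks 12, 24 and 36, exit at Week 48 (SAP 2.2, SAP 6.0).
- Exposure = last dose − first dose + min(84, exit − last dose + 1) (SAP 6.0).

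**Assumed**
- A share r of each arm, from 70% to 100%, enters and completes the open-label phase. The documents give no figure.
- All 259 per arm contribute the full 24 double-blind weeks, and those who do not continue contribute no open-label time.

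**Step 1: the plan's own formula for an on-schedule completer.**
Last dose − first dose = 36 × 7 = 252 days. Exit − last dose + 1 = 84 + 1 = 85, so the minimum is 84. Exposure = 252 + 84 = 336 days = 48.0 weeks, which falls in the top category.

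**Step 2: how much of that is placebo for a placebo-first subject.**
Double-blind doses only: 84 + 84 = 168 days = 24 weeks. The other 336 − 168 = 168 days (24 weeks, 50%) are BOTOX 195 U. One open-label dose gives 168 + 84 = 252 days = 36 weeks. So, with doses on schedule, a placebo-first subject can reach the two highest categories (36 to under 48 weeks, and 48 weeks or more) only through BOTOX doses.

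**Step 3: the whole arm, in subject-years (days ÷ 365.25).**
- BOTOX time in the placebo row: M = 259 × r × 168 / 365.25
- Placebo row: P = 259 × 168 / 365.25 + M = 119.1 + M
- Total BOTOX by first dose: B = 2 × (119.1 + M)
- True BOTOX: B + M

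| r | M | P | M/P | B | B + M | M/(B + M) |
|---|---|---|---|---|---|---|
| 100% | 119.1 | 238.3 | 50% | 476.5 | 595.6 | 20% |
| 70% | 83.4 | 202.5 | 41% | 405.0 | 488.4 | 17% |

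The 155 U row carries the same 83 to 119 subject-years of 195 U under a 155 U label. That does not change total BOTOX, only the split by dose.

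**Step 4: which adverse event tables cross Week 24.**
- Double-blind: ends the day before the Week 24 injection. No open-label time enters.
- Open-label: starts with the Week 24 injection. All treatment is 195 U, so a first-dose column is in effect a sequence group; only its label needs to say so.
- Entire study: Day 1 to Week 48. A placebo-first column holds up to 24 weeks on placebo and up to 24 weeks on 195 U.
- Each cycle: runs from one injection to the day before the next, so treatments are not mixed within a cycle.

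**The case against.** The strongest defence is that SAP 4.1 is a rule for dosing errors. It sits in the as-treated definition and settles the group of a subject who receives something other than the randomized treatment. SAP 10.1 groups subjects by treatment actually received, and SAP 4.3.2 already has sequence labels for the open-label phase, so the sponsor may well intend regimen columns after Week 24. SAP 6.0 does not say that total BOTOX excludes crossed-over subjects, and its sentence on the placebo group directly concerns the 12-week carry-forward. It also tabulates subjects treated at each cycle, and SAP 3.4 promises subject-level listings, so crossover dosing stays visible.

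Much of this stands. The intention may be sound, and the omission from total BOTOX depends on building that group by first dose. But 4.1 is the SAP's only definition of actual treatment, and it has no phase limit. Reading 10.1 as current treatment would contradict it. The 4.3.2 labels are not carried into the safety or exposure sections, and the 6.0 formula has no break at Week 24 under any reading.

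A reader might go further and infer that the mixed placebo column would conceal a BOTOX-related adverse event. The documents do not support that. The comparison with placebo belongs to the double-blind period, which contains no crossover time; Protocol 7.5 and SAP 10.2.5 both tie the treatment-versus-placebo analyses to those 24 weeks. In the entire-study table the BOTOX-first columns also accumulate open-label events, so setting a 48-week placebo-first column against a single fixed BOTOX rate would not compare like with like. Nor can it be said that all long-term safety tables report BOTOX as placebo: the open-label adverse event analyses are repeated specifically for subjects who receive open-label BOTOX.

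**Conclusion.** The point holds for the exposure summary in SAP 6.0 and the entire-study adverse event summary in SAP 10.1. Followed as written, a placebo-first completer is shown with 48 weeks of exposure in the placebo row, half of it BOTOX 195 U. The 24 weeks per subject follow from the schedule and the formula alone.

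The arm-level figures rest on the assumed 70% to 100% entry and completion and on full double-blind exposure for all 259: 41% to 50% of the placebo row would be BOTOX time. If total BOTOX is also formed by first dose, 17% to 20% of true BOTOX exposure would be missing from it.

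The double-blind safety comparison is not affected, per-cycle tables do not mix treatments, and open-label tables need only a clear sequence label. This is a reporting defect that should be corrected before the whole-study tables are produced; it does not threaten the efficacy analysis or the placebo-controlled safety comparison.

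**What to change.** - **SAP 4.1:** limit the first-dose rule to the double-blind phase.
- **SAP 10.1:** head the open-label and entire-study columns with the SAP 4.3.2 regimens (Placebo/195, 155/195, 195/195). Add one all-BOTOX adverse event summary that starts at each subject's first BOTOX dose: the first blinded injection for BOTOX-first subjects, the first open-label injection for placebo-first subjects.
- **SAP 6.0:** end placebo exposure the day before the first open-label injection. Show 155 U-first subjects' open-label time as 195 U or under the 155/195 regimen. Define total BOTOX so that placebo-first subjects count from their first BOTOX dose.

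The cost is SAP wording, table shells and the matching programming. Dose dates and event dates are already collected, so no new data are needed and study conduct does not change.

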4.2 Visit Windows

For data to be summarized on a per visit basis, the visit windows used for analysis are defined below.

Analysis Visit	Scheduled Visit	Nominal Day (Days Post Injection)	Case Report Form Window (Days Post Injection)	Diary Window (Days Post Injection)
Week -4	Visit 1	-28	Baseline Phase	-28 to -1
Week -4.1	Visit 1.1	n/a	Baseline overflow	< -28
Day 1	Visit 2	0	0	0
Week 4	Visit 3	28	1 to 42	1 to 28
Week 8	Visit 4	56	43 to 70	29 to 56
Week 12	Visit 5	84	> 70	57 to 84
Week 12.1	Visit 5.1	> 84	n/a	> 84
Week 16	Visit 6	28	1 to 42	1 to 28
Week 20	Visit 7	56	43 to 70	29 to 56
Week 24	Visit 8	84	> 70	57 to 84
Week 24.1	Visit 8.1	> 84	n/a	> 84
Week 28	Visit 9	28	1 to 42	1 to 28
Week 32	Visit 10	56	43 to 70	29 to 56
Week 36	Visit 11	84	> 70	57 to 84
Week 36.1	Visit 11.1	> 84	n/a	> 84
Week 40	Visit 12	28	1 to 42	1 to 28
Week 44	Visit 13	56	43 to 70	29 to 56
Week 48/Exit	Visit 14	84	> 70	57 to 84
Week 48.1/Exit	Visit 14.1	> 84	n/a	> 84

Note: Visit windows will be based on the time since the most recent injection (0 represents Day 1; negative value means the number of days prior to randomization, i.e., -1 represents the day prior to randomization (Day 1)).

In the protocol, the screening visit window is Day -35 to Day -28 and all post-randomization visits have a window of ± 3 days. The analysis windows are aligned with, but wider than, those specified by the schedule of visits and procedures in the protocol in order to include in analyses all study data that fall outside of protocol visit windows. In the event that two visits for a subject occur within the same visit window, if values observed on different study days or values are observed on the same study day with different time stamp, the last observation chronologically for each study phase (baseline, double-blind and open-label) will be used. If values are observed on the same study day without time stamp or values are observed on same study day with the same time stamp,

the average value will be used for analysis. For laboratory variables with qualitative values, if it cannot be determined which is most recent, then the worst measurement will be used. This rule will be applied separately for each variable for non-missing data only.

Diary data will be assigned per the diary window regardless of the actual visit schedule. Specifically, the diaries will be grouped into 28-day periods for baseline determination prior to randomization and for post treatment injection. This includes the baseline period, defined as the last 28 days of the baseline period (Day -28 to Day -1), and diary months will be the 4-week periods relative to the most recent injection (i.e., Days 1-28, 29-56, and 57-84). The third month of a given injection cycle could be truncated early, because it will end the day prior to a subsequent injection cycle, if that subsequent injection occurs prior to Day 85.

Also, some variables are not scheduled to be recorded at all visits. Visit windows for such visits will be concatenated into the next visit window. For example, for variables that are not to be recorded at Week 4 and Week 8, the analysis window for Week 12 will be widened to include the window for Week 4 and Week 8 (i.e., from Day 2 through the day of the Week 12 injection visit).

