5.6 Follow-Up After Subject Discontinuation of Study Drug or from Study

To minimize missing data for efficacy and safety assessments, subjects who prematurely discontinue study drug treatment should continue to be followed for all regularly scheduled visits, unless subjects have decided to discontinue study participation entirely (withdrawal of informed consent). Subjects should be advised on the continued scientific importance of their data even if they discontinue treatment with study drug early.

If a subject prematurely discontinues study participation (withdrawal of informed consent), the procedures outlined for the exit/PD visit (Week 48/Visit 14) should be completed as soon as possible, preferably within 2 weeks. In addition, if subject is willing, a 30-day follow-up phone call after the last dose of study drug may be completed to ensure all treatment-emergent AEs (TEAEs)/SAEs have been resolved.

In the event a subject withdraws consent from the clinical study, biomarker research will continue unless the subject explicitly requests analysis to be stopped. When AbbVie is informed the patient has withdrawn and no longer wishes biomarker samples research to continue, samples will not be analyzed, and no new biomarker analysis data will be collected for the withdrawn subject or added to the existing

data or database(s). Data generated from biomarker research, before subject withdrawal of consent, will remain part of the study results.

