6.2 Other Safety Data Collection

Columbia Suicide Severity Rating Scale (C SSRS)

The C-SSRS reports the severity of both suicidal ideation and behavior. Suicidal ideation is classified on a 5-item scale: 1 (wish to be dead), 2 (nonspecific active suicidal thoughts), 3 (active suicidal ideation with any methods [not plan] without intent to act), 4 (active suicidal ideation with some intent to act, without specific plan), and 5 (active suicidal ideation with specific plan and intent). The C-SSRS also captures information about the intensity of ideation, specifically the frequency, duration, controllability, deterrents, and reasons for the most severe types of ideation. Suicidal behavior is classified on a 5-item scale: 0 (no suicidal behavior), 1 (preparatory acts or behavior), 2 (aborted attempt), 3 (interrupted attempt), and 4 (actual attempt). More than one classification can be selected provided they represent separate episodes. For actual attempts only, the actual or potential lethality is classified for the initial, most lethal, and most recent attempts. Any subject who has suicidal ideation with intent (with or without plan), either via answering "yes" to question 4 and/or question 5 to the suicidal ideation section or "yes" to any question in the suicidal behavior section of the C-SSRS, or via clinical interview, will be evaluated immediately by the investigator and discontinued from the study. The AbbVie medical contact will also be notified. The subject should receive appropriate follow-up as in routine clinical practice. In addition, if the subject expresses suicidal ideation at any time during the study, the

investigator and the AbbVie medical contact should be notified immediately. Under no circumstances should a subject who has positively endorsed or expressed suicidal ideation be left alone, be allowed to exit the site, or go home before a qualified medical professional has evaluated the subject's risk.

The C-SSRS is administered by the clinician or trained personnel via subject interview in person or over the telephone, as applicable, at all study visits. At Visit 1 (screening), the C-SSRS will be completed for the subject's lifetime history and for the 6 months prior to screening. At all other visits the C-SSRS will be completed for ideation and behavior since the previous visit.

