10.5 Columbia-Suicide Severity Rating Scale (C-SSRS)

The C-SSRS responses will be recorded at each regular study visit: screening, Day 1, Week 4, Week 8, Week 12, Week 16, Week 20, Week 24, Week 28, Week 32, Week 36, Week 40, Week 44 and Week 48 visits. At Visit 1 (screening), the C-SSRS will be completed for the subject's lifetime history and for the 6 months prior to screening. At all other visits the C-SSRS will be completed for ideation and behavior since the previous visit.

Among the questions for each assessment time period (lifetime prior to screening, 6 months prior to screening, and since previous visit) are a set of 10 questions intended to elicit a yes or no response from the subject (as deduced by the investigator site's interview of the subject). Among those questions are 5 regarding suicidal ideation, arranged in order of increasing severity (1 wish to be dead, 2 non-specific active suicidal thoughts, 3 active suicidal ideation with any methods [not plan] without intent to act, 4 active suicidal ideation with some intent to act, without specific plan and 5 active suicidal ideation with specific plan and intent). Also included are 5 questions in the suicidal behavior section of the C-SSRS (0 no suicidal behavior, 1 preparatory acts or behavior, 2 aborted attempt, 3 interrupted attempt, 4 actual attempt).

C-SSRS data will be summarized separately for the following sets of responses: (1) lifetime prior to screening, (2) 6 months prior to screening, (3) baseline as reported under "since screening" at the randomization visit, (4) by visit for post-treatment visits (Week 4, Week 8, Week 12, Week 16, Week 20, Week 24, Week 28, Week 32, Week 36, Week 40, Week 44 and Week 48 visits), reported as "since last visit."

In each analysis table, subjects in the safety population will be grouped by treatment for analysis and will also be combined across treatment groups. Summary statistics will include the count and percentage of subjects for each of the 10 ideation and behavior categories separately and also for any ideation, for any behavior and for any ideation or behavior.

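### SAP 4.2 does not exempt the C-SSRS from its last-observation rule, so a later negative record in the same window can remove a positive screen from the only planned post-dose C-SSRS tables

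*SAP*

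**What the plan says.** **Selection rule.** SAP 4.2 assigns visits to windows by days since the most recent injection. The case report form windows in each injection cycle are 1 to 42, 43 to 70 and over 70 days. If two visits share a window, "the last observation chronologically for each study phase (baseline, double-blind and open-label) will be used", and "This rule will be applied separately for each variable for non-missing data only". The one worst-value provision is narrow: "For laboratory variables with qualitative values, if it cannot be determined which is most recent, then the worst measurement will be used". Nothing is said about the C-SSRS.

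**Instrument.** Protocol 6.2 gives the C-SSRS at every study visit. After screening the recall is short: "At all other visits the C-SSRS will be completed for ideation and behavior since the previous visit". SAP 10.5 repeats this.

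**After a positive screen.** Under Protocol 6.2 a subject with ideation 4 or 5, or any suicidal behavior, "will be evaluated immediately by the investigator and discontinued from the study". Protocol 5.6 says that exit/PD procedures for a subject leaving the study early "should be completed as soon as possible, preferably within 2 weeks". That sentence describes leaving the study, in parentheses, as withdrawal of informed consent.

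**Tables.** SAP 10.5 plans four sets of C-SSRS summaries: lifetime, 6 months before screening, baseline, and by visit after treatment. Within each, "Summary statistics will include the count and percentage of subjects for each of the 10 ideation and behavior categories separately", with rows for any ideation, any behavior, and either. There is no cumulative post-dose count. SAP 3.4 puts all safety data in subject-level listings.

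**The concern.** A last-value rule suits a measurement where the later value supersedes the earlier one. The C-SSRS after screening is not of that kind. Each record describes its own interval, so choosing the later of two records discards an interval instead of updating a status.

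The subjects most exposed are those with the most serious screens, because the protocol removes them from the study and an exit assessment may follow within days. If that assessment is negative and falls in the same window, the by-visit table shows the subject as negative. With no any-time post-dose row, no other C-SSRS table would show the event. The C-SSRS is a named safety endpoint and few such events should be expected, since inclusion criterion 19 excludes subjects with recent intent or behavior. One subject lost from a planned arm of 259 is only 1/259 = 0.4%, but it can turn a row from one to zero.

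**Working it through.** The documents state no figure for this point, so there is none to reproduce. The check asks how often an exit visit would fall in the same window as the positive screen.

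**Inputs from the documents**
- Nominal visits at 28, 56 and 84 days post injection, and the window limits above (SAP 4.2).
- Visit tolerance of 3 days either way (Protocol 4.1, SAP 4.2).
- Exit preferably within 14 days (Protocol 5.6).

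**Assumptions**
- Protocol 5.6 applies to subjects discontinued for a positive C-SSRS.
- The exit is on a later day than the screen.
- Every visit offset v = -3 to 3 and every delay d = 1 to 14 is equally likely, giving 7 x 14 = 98 pairs.
- Exit records map by days since injection.

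**First and second windows.** The upper limits are the nominal day plus 14: 28 + 14 = 42 and 56 + 14 = 70. A screen on day N + v and an exit on day N + v + d therefore share the window when v + d is at most 14. This fails for 1 delay when v = 1, for 2 when v = 2 and for 3 when v = 3. That is 6 failures, leaving 92/98 = 93.9%. It applies to all eight telephone visits (Weeks 4, 8, 16, 20, 28, 32, 40, 44).

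**Third window.** Above day 70 there is no upper limit unless another injection is given. For a Week 12 or Week 36 screen with no injection at that visit, 98/98 pairs share the window. If an injection is given, the count restarts and the exit falls in the next cycle.

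**Sensitivity to exit delay, telephone visits**

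| Longest delay (days) | Pairs sharing the window | Share |
|---|---|---|
| 7 | 49 of 49 | 100% |
| 14 | 92 of 98 | 93.9% |
| 21 | 98 of 147 | 66.7% |
| 28 | 98 of 196 | 50.0% |

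For the last two rows, 14 - v delays qualify for each v, and the sum over v = -3 to 3 is 98.

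**From shared window to lost positive.** The chance of loss is the product of three terms: a separate later record exists; it shares the window; it is negative. Only the second can be approximated from the documents. With the other two unknown, the product for a telephone-visit positive lies anywhere from 0 to the share in the table.

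**Effect of the fix.** If any 'yes' in a window is retained, the positive is kept in all 98 pairs at each nominal visit (294 of 294 over the three), whatever the exit answers.

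**The case against.** The case against a larger claim is good, and most of it stands.

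- **The second record is inferred.** A subject discontinued for a positive screen has not withdrawn consent, so applying Protocol 5.6 goes a step beyond its text. It is a reasonable step, because the documents give no other exit procedure. Exit could also take place on the day of the screen, leaving no later record. Two same-day records without distinct time stamps would be averaged under SAP 4.2, which has no meaning for yes/no items.
- **The exit record may have its own row.** SAP 4.2 labels one row Week 48/Exit, and Protocol 5.6 identifies the exit/PD visit with Week 48. If early exits map there, nothing is overwritten. The table note, which assigns by time since injection, points the other way. The SAP should say which holds.
- **The pathway is narrow.** Ideation 1-3 does not trigger this discontinuation. The next scheduled C-SSRS for those subjects is about four weeks later, normally in another window.
- **The event remains visible elsewhere.** It stays in the listings. Study discontinuations are tabulated by primary reason and arm (SAP 5.0), and an event reported as an adverse event would enter those tables.
- **The missing period table is a choice.** The SAP version history records that C-SSRS analyses by treatment period were removed in version 2.0. That explains the absence but does not repair the selection rule.

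A reader might also infer that the any-behavior row would count nearly everyone, because SAP 10.5 says "Also included are 5 questions in the suicidal behavior section of the C-SSRS (0 no suicidal behavior". That reading is strained: code 0 means none, and such a row would not ordinarily count it. It is a wording slip that adds little.

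**Conclusion.** The point holds in conditional form. As written, SAP 4.2 can drop a true positive C-SSRS from the by-visit tables, and SAP 10.5 has no other post-dose table that would show it. This requires a separate, later, negative record in the same window, with exit records mapped by days since injection.

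A reader might go further and infer that the exit visit routinely erases positives, that the by-arm tables are biased toward zero, or that 94% of serious positives would be lost. The documents support none of these. The 94% is a shared-window rate under assumed uniform timing, and the two-week limit is only a preference. Nothing in the plan indicates how often an exit C-SSRS would be negative, or how many positives to expect.

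No efficacy test or estimate is affected, nor is the handling of any subject. The weakness is in the by-arm reporting of a named safety endpoint. Confidence is high in the reading of the selection rule and moderate in how often it would matter.

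**What to change.** 1. **SAP 4.2:** exempt the C-SSRS from the last-observation and averaging rules, so that any 'yes' within a window is retained for that item. State whether early-exit records map by days since injection or to the Week 48/Exit row.
2. **SAP 10.5:** for each phase (double-blind, open-label), add by-arm counts of subjects with any post-dose ideation (1-5), ideation 4-5, and behavior (codes 1-4), using all scheduled, unscheduled and exit assessments. Naming codes 1-4 also settles the wording slip on code 0.

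The cost is a few sentences and one extra table per phase, with no new data. The downside is that this partly restores the by-period C-SSRS analyses removed in SAP version 2.0, so the SAP should give the reason.
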